The primary statistical analyses will assess the effectiveness of the full intervention (eTARGET) in producing smoking cessation compared to the no-treatment control (ASSESS) and the generic smoking cessation booklets(GENERIC). Based on prior published work ([name] et al., 2013), data from our cessation study (C.1.2.3), and considering that the sample will not be limited to treatment-seekers, we estimate no greater than 15% abstinence by 18 months in ASSESS, with at least 5% increments for GENERIC and eTARGET, respectively. We estimated sample size using GEESIZE version 3.1 (Rochon, 2003) with an AR(1) working correlation structure and coefficient of 0.7; adjusted alphas of .017 (ASSESS vs. eTARGET), .025 (ASSESS vs. GENERIC), and .05 (GENERIC vs. eTARGET) following Holm's procedure (Holm, 1979); and abstinence rates that increase from 6 to 18 months, then remain stable through 30 months. Randomizing 2065 participants based on 1:2:2 relative sizes (413 to ASSESS; 826 to GENERIC, and 826 to eTARGET) ensures ≥80% power for all contrasts. We plan to recruit 580, 1160, and 1160 individuals, respectively, in expectation of 17% attrition after baseline assessment, as observed in our prior study.

We initially planned to recruit 500, 1000, and 1000 individuals, respectively, in expectation of 17% attrition after baseline assessment, as observed in our prior study. Based on return rates of the 3-month survey for the first 575 study participants, we now expect 27.5% attrition after baseline. Therefore, we plan to recruit 2900 individuals (400 more than initially planned) with 580, 1160, and 1160 individuals in the ASSESS, GENERIC, and eTARGET conditions, respectively. This will ensure the same sample size for statistical analysis at the higher-than-expected attrition rate.

C.6.3. Data Analysis Overview

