Participants will be randomized into the three conditions using balanced-permuted block randomization with a block size of 10 (2-4-4). Analyses will be conducted with SAS version 9.3 and Mplus Version 7 (Muthén & Muthén, 2008). Frequency distributions and contingency table analyses will be used as a point of departure for more advanced analyses. Multiplicity will be legitimately adjusted as needed for Aim 2, but not for the secondary or exploratory analyses. We will perform attrition analyses, using survival analysis, to test whether the attrition rate differs across intervention arms, if participants and dropouts differ on key variables, and if such variables moderate attrition differences across arms. The median time to attrition and its 95% confidence interval, will be summarized by intervention arm using the Kaplan-Meier method with log-rank test. Any significant variables on those attrition patterns in multivariable Cox Proportional Hazards (PH) models will be accounted for during multiple imputations as well as in the main analysis.

To manage missing data, multiple imputation under the Missing at Random assumption will be applied using a Markov Chain Monte Carlo method (Shafer, 1997) via PROC MI in SAS, given the expected large number of non-monotonic missing data patterns. Preliminary analyses will determine auxiliary variables (e.g., baseline measures that predict smoking status at follow-up) to be used. A post hoc approach (Rubin, 1987) will address the influence of Missing Not at Random (MNAR) on smoking status (i.e., missing is due to smoking). Sensitivity analyses will be performed to assess alternative multiple imputation techniques upon the extent of MNAR influences.

C.6.4. Analytic Plan for Addressing Specific Aims.

C.6.4.1. Specific Aim 1 (see C.2.3.2.) and Aim 3 (see C.5.)

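### C.6.2 ties Holm's three alphas to named arm pairs and no section states the analysis rule; Shaffer's step-down for three pairwise contrasts would settle this at no cost in error rate

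*Combined protocol and SAP*

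**What the plan says.** C.6.2 (Sample Size and Study Power Analysis) runs a GEE sample-size program with an "AR(1) working correlation structure and coefficient of 0.7" and "adjusted alphas of .017 (ASSESS vs. eTARGET), .025 (ASSESS vs. GENERIC), and .05 (GENERIC vs. eTARGET", "following Holm's procedure (Holm, 1979". The assumed rates are: "we estimate no greater than 15% abstinence by 18 months in ASSESS, with at least 5% increments for GENERIC and eTARGET, respectively". The analysed sizes are "413 to ASSESS; 826 to GENERIC, and 826 to eTARGET", which the section says "ensures ≥80% power for all contrasts".

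C.6.2 opens by describing the primary analyses as eTARGET against each of the other two arms. It still gives the third pair an alpha, and C.3.1 and C.3.3.2 commit to testing that pair too.

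On the analysis itself, C.6.3 says only: "Multiplicity will be legitimately adjusted as needed for Aim 2, but not for the secondary or exploratory analyses". C.6.4.2 describes generalized score tests of pairwise and time contrasts from the GEE model, and names no procedure, order or level.

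**The concern.** Holm's procedure ranks the observed p-values and compares the smallest with .05/3, the next with .05/2 and the largest with .05. Which pair meets which level is known only once the data are in. C.6.2 fixes this in advance by arm pair. Because C.6.3 and C.6.4.2 give no rule, that sentence is the only place where a multiplicity method appears.

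Two things follow. The rule for the main comparisons is open until someone chooses it, possibly after seeing the data. The power calculation was also not done under the procedure it cites.

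There is a missed opportunity as well. Three pairwise hypotheses on three arms are logically linked, and a step-down rule that uses the link is never less powerful than Holm, with the same error control.

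**Working it through.** **1. The plan's own figures.** .05/3 = .0167 (printed as .017), .05/2 = .025 and .05/1 = .05, so the alphas are Holm's. The sample size cannot be reproduced, because the rates at 6 and 12 months, the GEE contrast and the sidedness are not given. It is attainable. Assume ASSESS rates of 5/10/15/15/15% over five visits to 30 months, with +5 points in GENERIC and +10 in eTARGET, AR(1) 0.7, a time-averaged logit contrast and two-sided tests. ASSESS vs GENERIC at .025 then needs 411 in ASSESS (the plan has 413), and power is 99.9% (ASSESS vs eTARGET), 80.2% (ASSESS vs GENERIC) and 91.9% (GENERIC vs eTARGET).

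**2. Expected order at 15/20/25% and 413/826/826.** z = difference / sqrt(p1(1-p1)/n1 + p2(1-p2)/n2), for one visit:

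- ASSESS vs GENERIC: .05 / sqrt(.15×.85/413 + .20×.80/826) = .05/.02241 = 2.23
- GENERIC vs eTARGET: .05 / sqrt(.20×.80/826 + .25×.75/826) = .05/.02051 = 2.44
- ASSESS vs eTARGET: .10 / sqrt(.15×.85/413 + .25×.75/826) = .10/.02315 = 4.32

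ASSESS vs GENERIC is the weakest because ASSESS is half the size. The margin is small: in simulation this pair has the largest p-value in about 55-57% of trials, depending on the variance assumed. The order is not guaranteed either. With equal 5-point steps the two variances are equal when 2p(1-p) = (p+.10)(.90-p), that is p² - 1.2p + .09 = 0, or p = .080. Below an ASSESS rate of about 8% the order reverses on this scale.

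**3. Power by rule at the planned rates.** Arm estimates were simulated as normal with the variances above times a factor. Factor 1 is a single visit. Factor 0.678 is the mean of four visits under AR(1) 0.7 with a constant gap: [4 + 2(3×.7 + 2×.49 + .343)]/16. Factor 0.52 gives ASSESS vs GENERIC 80% power at .025: the z needed is 2.241 + 0.842 = 3.083, and (2.231/3.083)² = 0.52.

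| Variance factor | Contrast | Pair-fixed alphas | Holm | Shaffer |
|---|---|---|---|---|
| 1 | ASSESS vs GENERIC | 49.6% | 56.3% | 60.5% |
| 1 | GENERIC vs eTARGET | 68.3% | 63.5% | 67.9% |
| 0.678 | ASSESS vs GENERIC | 68.0% | 76.1% | 77.4% |
| 0.678 | GENERIC vs eTARGET | 84.2% | 82.8% | 84.1% |
| 0.52 | ASSESS vs GENERIC | 80.0% | 86.6% | 86.9% |
| 0.52 | GENERIC vs eTARGET | 92.0% | 91.7% | 92.0% |

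Only the last pair of rows agrees with the plan's statement of at least 80% for every contrast. There the fixed .025 understates the Holm power of ASSESS vs GENERIC by about 7 points, and the fixed .05 overstates that of GENERIC vs eTARGET by about 0.3.

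**4. Why Shaffer's rule is valid.** Write the nulls as A=G, G=E and A=E. Any two imply the third, so if one is false at most one other can be true. After a first rejection at .05/3, at most one true null remains, and each remaining contrast can be tested at .05. Simulated familywise error is 4.4% when all arms are equal, and its maximum over the global and partial nulls is .050 within simulation error. In no simulated trial did Holm reject a contrast that Shaffer did not.

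**5. Pair-fixed alphas as decision thresholds.** With all arms equal, applying them in parallel gives a familywise error of about 8.0% (the printed alphas sum to .092). Applying them as a gatekept sequence in the listed order gives 1.7%.

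**6. If GENERIC equals another arm (variance factor 0.678).**

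- 15/15/20%: eTARGET vs ASSESS goes from 66.8% under Holm to 73.7% under Shaffer.
- 15/20/20%: each contrast against ASSESS goes from 65.5% to 69.8%.

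**The case against.** The alphas are inputs to a sample-size program that needs one level per contrast. Assigning Holm's levels in an anticipated order is an ordinary planning simplification, and the same sentence names Holm. This stands, and it limits the point in three ways.

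- A reader might infer that the trial will run at 8% familywise error. The documents do not support that: nothing says that final p-values will be compared with pair-fixed thresholds, and gatekept in the listed order the same alphas are conservative.
- A reader might infer that the statement of at least 80% power is false. That is not shown either. If ASSESS vs GENERIC has 80% power at .025, true Holm gives about 87% and 92% on the two 5-point contrasts.
- A reader might call the planned order simply wrong. It is only the less likely of two close orders. C.6.2 gives 15% as a ceiling and 5 points as a minimum, so the order is not fixed by the plan.

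It is also fair to say that Holm is valid and that choosing it is no error. The single-visit gains of about 4 points do not describe the planned longitudinal analysis, and C.6.2 does not assume 15/15/20 or 15/20/20. Shaffer's rule is never weaker than Holm, but it can be marginally weaker than the parallel pair-fixed rule on GENERIC vs eTARGET (67.9% against 68.3% at one visit). That rule does not control familywise error.

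Finally, error control covers one family of three contrasts. Specific Aim 2 hypothesises effects at 6, 12, 18 and 24 months, and C.6.4.2 tests time intervals as well, so the fix must say which contrast the family uses.

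**Conclusion.** C.6.2 describes Holm in a form that is not Holm, and the analysis sections leave the rule unstated. The defect lies in specification; it does not show an invalid test or an undersized trial. At the planned inputs, holding ASSESS vs GENERIC at .025 is conservative.

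Replacing the named procedure with Shaffer's step-down is a free improvement. It gains about 0.3 points over Holm on the two 5-point contrasts at the planned rates and power, and about 4-7 points on contrasts against ASSESS if the generic booklets match either no treatment or the targeted booklets. The larger gain falls on eTARGET vs ASSESS when GENERIC does nothing.

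These sizes rest on two-sided tests, normal arm estimates and assumed variance factors, since the plan does not give the 6- and 12-month rates or the GEE contrast. The validity of the step-down does not depend on those assumed values.

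**What to change.** In C.6.2, remove the pair-specific alphas. In C.6.2 and C.6.3, state that:

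- the confirmatory family is the three pairwise arm contrasts, all on one prespecified GEE contrast of 7-day tobacco abstinence (the same time point or the same time average for every pair);
- the contrasts are ordered by observed p-value, the smallest is tested at .0167 and, if it is rejected, both others are tested at .05 (Shaffer's step-down for three pairwise hypotheses);
- if the smallest is not rejected, testing stops;
- comparisons at other time points lie outside this family and carry no familywise claim.

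Using one contrast definition for every pair is essential, because the logical link between the three nulls holds only then. Restate the power of each contrast under this procedure, giving the assumed rate at each visit and the sidedness.

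The cost is one paragraph of text and a rerun of the power calculation. It needs no further participants and gives up no error control for the family.

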C.4.1.3. Follow-Up Assessments. Participants will be sent follow-up assessments (by mail or email link) at 3-month intervals through 24 months, as indicated in Table 3. The length of the follow-up (24 months post-enrollment) was calculated by adding the standard 6 months after the end of the eTARGET intervention. We deliberately keep each follow-up assessment brief to minimize participant burden and consequent attrition. Each of these follow-ups will include an assessment of the use of tobacco products, e-cigarettes, pharmacotherapies, and other tobacco cessation aides or services since the previous contact. These data will constitute the Abbreviated Follow-Ups, and will be sufficient for calculating treatment outcomes as well as for the longitudinal tracking of cigarette and e-cigarette usage for the secondary aim. Full Follow-Ups at 6, 12, 18, and 24 months will include most of the questionnaires from the baseline assessment, as well as additional domains, including evaluation of the intervention (Client Satisfaction Questionnaire; Attkisson & Greenfield, 1994), self-reported use of the material (i.e., how much they read, how often they refer back, how much it affected their behavior), current intentions to guit smoking and to guit e- cigarettes, and the three motivationrelated scales administered at baseline. The 24 month follow-up will also include an 12-item measure of health outcomes (SF-12[™] Health Survey; Ware, J E, Kosinski, M, Keller, S D., 1995), 2001). Research staff will attempt to contact participants to complete any missing data on the completed baseline and follow-up assessments.

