At each assessment point we will calculate point-prevalence abstinence rates (for tobacco smoking as well as e-cigarette use) using 7-day, 30-day, and 90-day criteria. Point-prevalence measures are best for capturing the dynamic nature of cessation, maintenance, and relapse. The 7-day criterion will serve as our primary outcome index. Continuous abstinence is not feasible because guit dates will be highly variable across participants, and also because one goal of the intervention is to encourage lapsers to guit again (recycle). We need our outcome measures to reflect these changes in smoking status over time. However, the 30-day and 90-day point-prevalence abstinence criteria also reflect more prolonged abstinence than the 7day criterion usually used in treatment studies (Velicer et al., 1992). We will also compare groups on continuous measures, such as current smoking rate (cigarettes/day), months of smoking during the follow-up period, length of current abstinence period, and latency from quit date to relapse. Outcomes will be reported that account for missing follow-up data using both multiple imputation (MI) and intent-to-treat (ITT) approaches.

C.5. Cost-Effectiveness Analysis (Aim 3)

The relative effectiveness and costs of the intervention compared to standard care will be measured based on the health care system perspective. Using the trial endpoint results, effectiveness will be predicted in terms of smoking cessation and translated into life years and quality adjusted life years (QALY) based on published associations between smoking cessation and long-term health outcomes (Cohen & Fowler, 1993; Torrance, 1986). Costs include the intervention costs, collected prospectively, and lifetime costs of reduced medical expenditures attributable to smoking cessation, that will be modeled using published estimates (e.g., Berman et al., 2013; Cowan & Schwab, 2011; Fishman et al., 2003; Hockenberry et al., 2012; Hodgson, 1992; Oster et al., 1984). No out-of-pocket costs or transfer payments (i.e., increased social security due to longevity) will be incorporated into the analysis, because they do not fall within the system perspective. In addition, costs associated only with research (e.g., mailing of assessments) will be excluded. Monetary values will be inflation adjusted, and all outcomes will be presented in discounted and undiscounted values.

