C.6.4.2. Specific Aim 2. Generalized estimating equations (GEE) will be used to fit populationaveraged models to handle the longitudinally measured binary outcomes, with the main covariates of intervention conditions, time (months from baseline), and the interaction of condition and time. Potential confounding variables (e.g., group differences in demographic, smoking history, or pharmacotherapy use) that appear despite randomization will be adjusted for in the model. Pair-wise condition and time interval comparisons will be tested using the generalized score statistics from GEE models by utilizing the contrast statements. Further, the generalized linear mixed effects models with a logit link function will be expanded, including the participant-specific intercept and slopes as the random effects in the model. Moderators (e.g., gender, SES, quitting motivation, nicotine dependence, magnitude of e-cigarette use, expectancies)will be tested via interactions with condition and condition x time. *Mechanisms of change associated with treatment*

will be tested (e.g., motivational measures, intervention usage, e-cigarette usage) via mediation analysis, performed using Hayes' (2009) "Indirect" macro within SAS. The approach described above will be used to evaluate the primary outcome of smoking cessation as well as the secondary outcome of e-cigarette cessation.

We will extend our analysis to lapse/recovery models using the Kaplan-Meier method with log-rank test for the stratified sub-groups (e.g., lapsed and recovered groups) to test the effect of intervention condition and Cox PH models controlling potential confounding variables.

To capture proportional shifts in cigarette vs. e-cigarette use, we will create a response variable with multiple levels for each follow-up assessment reflecting the relative level of e-cigarette to cigarette use, referenced against baseline use of each product. The multi-level outcome variable will be fitted using a logistic analysis on the generalized logits to test if the interventions have a significant impact on these shifts.

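### Missing yes/no abstinence is imputed by PROC MI's normal-model MCMC method, with no rule for turning the draws into the 0/1 values the GEE needs; logistic FCS would avoid that step

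*Combined protocol and SAP*

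**What the plan says.** Section C.4.2 makes the 7-day criterion the primary index and states that "At each assessment point we will calculate point-prevalence abstinence rates". Outcomes are to be reported under both multiple imputation and ITT. Section C.4.1.3 says that even the abbreviated follow-ups "will be sufficient for calculating treatment outcomes", so abstinence is available at all eight follow-ups, from 3 to 24 months.

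For missing values, Section C.6.3 says that "multiple imputation under the Missing at Random assumption will be applied using a Markov Chain Monte Carlo method", in PROC MI, and gives the reason as "given the expected large number of non-monotonic missing data patterns". It adds that "Sensitivity analyses will be performed to assess alternative multiple imputation techniques upon the extent of MNAR influences".

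The analysis model is in Section C.6.4.2: "Generalized estimating equations (GEE) will be used to fit populationaveraged models to handle the longitudinally measured binary outcomes". Pairwise comparisons are to be "tested using the generalized score statistics from GEE models by utilizing the contrast statements". A second model follows: "the generalized linear mixed effects models with a logit link function will be expanded". The same approach is applied to e-cigarette cessation.

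Neither section mentions rounding, a threshold, a logistic or categorical imputation model, or any other link between the imputed draws and the binary GEE.

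**The concern.** PROC MI's MCMC method treats the imputed variables as jointly normal. Applied to a 0/1 indicator, it returns values such as -0.2, 0.37 or 1.1, which a binary GEE cannot take as they stand. Someone must convert them, and the plan does not say how. Even if missing at random holds exactly, the MI-based odds ratio then depends on the rule chosen, and the choice could be made with the data in view.

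The alternative imputation techniques mentioned in C.6.3 are unnamed and are tied to departures from missing at random, so they do not fill the gap. The reason given for MCMC does not require a normal model either, because FCS also handles non-monotone patterns.

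**Working it through.** **Amount imputed.** C.6.2 expects 27.5% attrition. The recruitment target reproduces: 2065 / (1 - 0.275) = 2849, against 2900 planned, and 2900 × 0.725 = 2102. The share to impute is 2900 × 0.275 ≈ 798 participants per visit if 27.5% holds throughout. That is an assumption, because the figure comes from 3-month survey returns. In the team's earlier cessation trial (C.1.2.3, Table 1), 1191 of 1874 responded at 18 months: (1874 - 1191) / 1874 = 36% missing.

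**Planned effect.** With 15% in ASSESS and 25% in eTARGET, the odds ratio is (0.25/0.75) / (0.15/0.85) = 1.89 and the log odds ratio is 0.636. With 580 and 1160 participants and no missing data, SE = √[1/(580 × 0.15 × 0.85) + 1/(1160 × 0.25 × 0.75)] = 0.135.

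**Main simulation.** This used eight follow-ups, arms in the ratio 580:1160:1160 at 8 times planned size to reduce noise, 24 replicates per scenario, and 27.5% missing per visit at random given the observed data. From the plan: rates of 15/20/25% from 18 months and a correlation of 0.7. Assumed: rates at months 3, 6, 9, 12 and 15 equal to 50, 65, 74, 82 and 91% of the 18-month rates; one baseline covariate predicting both abstinence and missingness; and every conversion rule, since the plan states none.

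- Scenario A: intermittent missingness, correlation 0.70 over 6 months, 3% miss every visit.
- Scenario B: same correlation, mostly the same people missing, 16% miss every visit.
- Scenario C: intermittent missingness, correlation 0.70 over 3 months (C.6.2 does not give the interval).

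At 24 months, 37-39% of the normal draws lay outside 0-1. Changes in the eTARGET versus ASSESS log odds ratio, against full data in the same replicate (Monte Carlo SE 0.5-1.0%):

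| Method | A | B | C |
|---|---|---|---|
| Normal model, round at 0.5 | -4.2% | -6.4% | -5.6% |
| Normal model, adaptive rounding | -3.4% | -5.5% | -4.7% |
| Normal model, truncate, then random 0/1 draw | -11.7% | -14.0% | -12.9% |
| Normal model by arm, round at 0.5 | +1.6% | +0.9% | not run |
| Logistic FCS | -0.4% | +2.8% | -0.3% |

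Applied to the planned odds ratio of 1.89:

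- 0.5 rounding: exp(0.636 × 0.958) = 1.84 to exp(0.636 × 0.936) = 1.81.
- Random draw: exp(0.636 × 0.883) = 1.75 to exp(0.636 × 0.860) = 1.73.
- By arm: exp(0.636 × 1.009) = 1.90 to exp(0.636 × 1.016) = 1.91.

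Arm rates (ASSESS/GENERIC/eTARGET) rose by 0.6/0.5/0.4 to 1.0/0.8/0.7 points with common-covariance 0.5 rounding, and by 1.8 to 2.6 points with the random draw. FCS was within 0.2 point in A and C and 0.4-0.5 point low in B. A one-pass sequential logistic fill-in stayed within 0.16 point and 1.5%.

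**Second simulation.** This used 188 trials at the planned arm sizes and four follow-ups, with 6- and 12-month rates assumed at 60% and 80% of the 18-month rates. About 41% of draws fell outside 0-1. The last column is computed from the average 18-month rates.

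| Method | ASSESS / eTARGET, % | Difference, points | Log odds ratio |
|---|---|---|---|
| Full data | 15.11 / 25.03 | 9.92 | 0.629 |
| Normal, unrounded | 14.81 / 25.06 | 10.25 | not applicable |
| Normal, round at 0.5 | 15.82 / 25.47 | 9.65 | 0.598 (-4.9%) |
| Normal, adaptive rounding | 15.37 / 24.91 | 9.54 | 0.602 (-4.2%) |
| Logistic FCS | 15.14 / 25.02 | 9.89 | 0.626 (-0.5%) |

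**Third simulation.** With four visits, about 28% missing and 12% missing every visit, the log odds ratio changed by about -5% with 0.5 rounding and -13% with the random draw; FCS stayed within about 1%.

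**The case against.** **The imputed variable is not named outright.** C.6.3 speaks of missing data in general, and C.4.2 also lists continuous measures such as the length of the current abstinence period. If one of those were imputed, the 7-day criterion would act as the threshold. That is possible, but it too would need a stated rule. C.6.3 mentions only smoking status when it describes the auxiliary variables and the sensitivity analysis.

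**The effect is small.** Common-covariance rounding shifts the log odds ratio by 0.034 × 0.636 = 0.022 to 0.064 × 0.636 = 0.041, or 0.16 to 0.30 of the no-missing-data SE, and towards the null. The largest shifts come from the random-draw rule, which nothing in the plan suggests. Coverage, type I error and power were not simulated. All of this stands and limits the priority.

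**FCS does not win everywhere.** In scenario B, FCS is off by +2.8%, while the normal model run by arm with 0.5 rounding is off by +0.9%. Scenario B may be realistic, since the 27.5% reflects non-return of the first survey; whether those people return later is unknown. This stands as a limit on FCS and is why a check is built into the fix. It does not rescue the plan, which specifies neither arm-specific imputation nor rounding. A rounding rule fixed in advance would remove the discretion, as a lesser remedy.

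**Exposure is partial.** ITT does not use this imputation model, and the mixed model may not. That is true, but the MI result is one of the two that the plan commits to reporting.

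**Separate logistic imputations could contradict each other**, for example abstinent for 90 days but not for 7. This is fair, and a consistency rule is needed.

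**Conclusion.** The concern holds. The named imputation method does not produce the kind of value the primary model requires, and the plan does not say how the gap is bridged. Across the conversion rules tried, the planned odds ratio of 1.89 becomes anything from about 1.73 to 1.91, so both the size and the direction of the error depend on an unstated choice. The simpler rules under a common covariance give about 1.81 to 1.85 (lowest from 0.5 rounding at -6.4%, highest from adaptive rounding at -3.4%: exp(0.636 × 0.966) = 1.85).

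These sizes rest on the planned rates, 27.5% missing at every visit, missing at random, and assumed early-visit rates and missingness patterns. The sample size is not affected and no change of conclusion is shown. This is a worthwhile, inexpensive improvement of minor-to-moderate priority.

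**What to change.** In Section C.6.3, replace the MCMC method with FCS using a logistic model for abstinence at each of the eight follow-ups. The predictors would be arm, abstinence at the other visits, the baseline auxiliaries and the attrition predictors. Then add:

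- a check against a sequential logistic fill-in if many participants miss every follow-up;
- a rule that keeps the nested 7-, 30- and 90-day indicators consistent;
- the pooling method: GEE log odds ratios with robust standard errors combined by Rubin's rules, or the D2 rule if the score statistics of C.6.4.2 are kept.

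If the MCMC method is retained, state in advance which variable is imputed, whether imputation is by arm, and the exact conversion rule.

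The cost is a little more programming, a paragraph of SAP wording, a safeguard against perfect prediction, and a check that SAS 9.3, the release named in C.6.3, offers the method; if not, a newer release is needed. There is no cost in data or to participants.
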